3.7 Monitoring

3.7.1 Data Quality Monitoring

The Chief Researcher will periodically monitor the completed study documents and the database entries. If any problems are found with completion of study documents, training sessions will be arranged in the Department of Anaesthesia.

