3.3.2 Blinding

The patient will be blinded to the group they have been randomised to, as the vapour will only be started after induction of anaesthesia. The research assistant administering the post-operative QoR-15 will be blinded to the intervention.

The treating anaesthetist, the Chief Researcher and theatre staff will not be blinded to the intervention, as this would not be practical. All treating anaesthetists and theatre staff will be strongly inculcated not to disclose the allocation status of the participant at any time prior or after the general anaesthetic.

The piece of paper indicating the group will be attached to the Case Report Form. The Case Report Form will be collected by the Chief Researcher and will not be in the patient's file where it may unblind the patient or research assistant.

There are no circumstances under which unblinding will be permissible.

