3.5.2 Data Storage

Study documents will be stored securely by the Chief Researcher. Documents will be kept in a dedicated lever-arch file and will be arranged sequentially according to study number. All study documents relating to a single patient will be stored together.

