3.7.2 Interim Analysis

Interim analysis will not be done.

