3.8 Reliability and Validity

- Validity:
 - Internal validity should be assured on the basis that the anaesthetic techniques will be unchanged between the two groups, except for the anaesthetic vapour. Maintaining the end-tidal vapour concentration at 1MAC for both drugs will prevent disproportionate effects of one drug over the other. The patient population should be homogenous, as only ASA I and II patients presenting for ophthalmological surgery will be included in the study.
 - The chief researcher will counsel each treating anaesthetist prior to them starting a study case to ensure that they follow the required standardised anaesthesia protocol. This will reduce the

chance of protocol violations occurring. Any deviations from the standardised protocol will be recorded on the Data Collection Form and will be assessed by the chief researcher.

- Construct and content validity are assured on the basis that the QoR-15 has been extensively validated in many different languages and for many different surgery types.
- Data on the Case Report Forms will be inspected for completeness as per section 4.3.5. Incomplete cases will be excluded from analysis.

- Reliability:

- The QoR-15 is a reliable tool to use. During development of the tool, the internal consistency was measured using Cronbach α and split-half reliability, both of which had satisfactory results.
- Reproducibility of the QoR-15 was excellent, and exceeded that reported for the QoR-40, indicating that the QoR-15 score can be interpreted with confidence.

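### Deviations are assessed by an unblinded person who has access to the day-1 score, with no criteria, no timing rule and no as-randomised analysis set

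*Combined protocol and SAP*

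**What the plan says.** **Knowledge of arm.** Section 3.3.2 states: "The treating anaesthetist, the Chief Researcher and theatre staff will not be blinded to the intervention, as this would not be practical". It adds: "The piece of paper indicating the group will be attached to the Case Report Form". The Chief Researcher collects that form.

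**Access to outcome.** Section 3.4.2 lists the post-operative QoR-15 among the study documents. Under 3.5.2 the Chief Researcher holds these documents, and "All study documents relating to a single patient will be stored together". Under 3.7.1, "The Chief Researcher will periodically monitor the completed study documents and the database entries". The day-1 score is not exempted from either arrangement.

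**Assessment of deviations.** Section 3.8 says: "Any deviations from the standardised protocol will be recorded on the Data Collection Form and will be assessed by the chief researcher". It gives no criteria, time limit or masking.

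**Effect on who is analysed.** The WHO data set (1.1.2) lists treatment outside the prescribed protocol as an exclusion. Section 3.2.5 justifies the protocol changes partly because they will avoid excluding such cases. The eligibility list in 3.2.2 has no such criterion. Incomplete records are an exclusion in 3.2.2, and 3.8 removes incomplete cases from the analysis. Section 3.6 names no analysis set, and the SPIRIT checklist (6.1) marks item 20c, on the analysis population, as not applicable.

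**The concern.** The design blinds the patient and the day-1 observer so that the score is recorded without knowledge of the arm. That does not protect the next step, which is deciding whose score enters the comparison. If off-protocol patients can be dropped, the person who classifies a case as off-protocol affects membership of the analysis set. Here that person knows the arm and can see the outcome, and no rule fixes the classification beforehand.

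At stake is the credibility of the primary comparison. Excluding patients after randomisation with arm and score in view can bias the difference in either direction. A reader of the final report could not tell whether it had, because the plan contains neither a dated classification nor an as-allocated analysis to compare against.

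**Working it through.** **1. What the documents establish and what they leave open**

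| Element | Source | Status |
|---|---|---|
| Assessor knows the arm | 3.3.2 | Stated |
| Assessor has access to the day-1 score | 3.4.2, 3.5.2, 3.7.1 | Follows from filing and monitoring |
| Assessor judges deviations | 3.8 | Stated |
| Criteria, timing, masking of that judgement | 3.8 | Absent |
| Off-protocol cases excluded | 1.1.2 and 3.2.5, against 3.2.2 | Inconsistent |
| Who decides on exclusion | 3.8 | Not stated |
| Analysis population | 3.6; SPIRIT item 20c in 6.1 | Undefined |

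The opportunity for informed exclusion follows from these sections taken together. Section 3.7.1 alone would not show it.

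**2. The plan's own figure**

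Inputs from 3.2.8: difference 8, SD 18.5, two-sided 5%, power 80%.

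Normal approximation: n = 2 × (1.960 + 0.842)² × 18.5² / 8² ≈ 84 per arm. The exact noncentral t calculation gives 85 per arm, with power 0.800. The stated 85 reproduces, so these inputs serve for the illustration.

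**3. Illustration of size**

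The documents give no deviation rate, so rates of 5%, 10% and 15% per arm are assumed. Further assumptions: no true effect, normal scores with SD 18.5, 85 per arm, and deviation unrelated to score. Two rules were simulated, with 40,000 trials at each rate:

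- *Neutral:* every deviator is dropped.
- *Selective (worst case modelled):* only desflurane deviators scoring below the mean and isoflurane deviators scoring above it are dropped.

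The bias under the selective rule can be checked by hand. A fraction f/2 of each arm is removed, and those removed lie on average SD × √(2/π) = 18.5 × 0.798 = 14.76 points from the mean. Bias in the difference = 2 × (f/2) × 14.76 / (1 − f/2):

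- f = 0.05: 2 × 0.025 × 14.76 / 0.975 = 0.76
- f = 0.10: 2 × 0.05 × 14.76 / 0.95 = 1.55
- f = 0.15: 2 × 0.075 × 14.76 / 0.925 = 2.39

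| Assumed deviation rate | Type I error, neutral | Type I error, selective | Simulated bias, points |
|---|---|---|---|
| 5% | 0.050 | 0.059 | 0.73 |
| 10% | 0.050 | 0.083 | 1.53 |
| 15% | 0.049 | 0.131 | 2.41 |

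The formula and the simulation agree to within about 0.03 points. Under these assumptions the inflation comes entirely from selecting on arm and score. Dropping deviators does not by itself cause it.

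Neutral exclusion still costs power. With 81, 76 or 72 left per arm, power for a difference of 8 falls from 0.800 to 0.781, 0.754 or 0.731.

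**The case against.** The strongest reply is that the documents describe access and no misuse of it. Four parts of it stand.

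- **Monitoring.** A reader might infer that monitoring by an unblinded person conflicts with "Interim analysis will not be done" in 3.7.2. It does not. Section 3.7.1 concerns data quality, and its only stated consequence is this: "If any problems are found with completion of study documents, training sessions will be arranged in the Department of Anaesthesia". No comparison by arm, stopping or adaptation is described, and the statistician receives no data until collection ends (3.3.1).
- **Sequence.** A reader might also infer that the Chief Researcher reviews scores and arms side by side and then judges deviations. No section says so. The treating anaesthetist makes the first adherence entry in Section B of the Case Report Form (3.4.3, 6.7). That form is handed in at the end of the procedure or left in the recovery-room box (6.6), normally before a day-1 score exists. Only the timing of the later assessment is open.
- **Completeness.** The blinded assistant checks day-1 forms at the bedside, and gaps in Section B are filled from sources in a set order (3.5.3). This part is largely rule-based.
- **Size.** Larger inflation results from supposing that extreme scorers could be removed freely from either arm. The documents give no ground for that, because removal would have to rest on a recorded deviation or an incomplete record.

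None of this supplies the missing safeguard. The adherence entry is a yes/no item with free text, the assessment that follows has no criteria or deadline, and the plan does not settle whether an off-protocol patient is analysed.

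**Conclusion.** The point holds as a gap in the analysis population and in the assessment of deviations. Exclusions after randomisation could be made with arm and outcome known. The documents do not show that they will be, and nothing suggests intent.

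The size is illustrative: type I error of about 6% to 13% in place of 5%, and a bias of about 0.7 to 2.4 points against a minimal clinically important difference of 8. These figures rest on assumed deviation rates of 5% to 15% and on the selective pattern described. Exclusion without regard to score leaves type I error at 5% under the same assumptions. This should be corrected, because the risk bears on the primary comparison and the correction is cheap.

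**What to change.** **Section 3.8.** State the criteria for a deviation. Classify every deviation and eligibility question from Sections A and B of the Case Report Form, then date and lock the result before that patient's day-1 QoR-15 is available to the Chief Researcher. Until then the assistant files day-1 forms separately, and 3.5.2 and 3.7.1 should say so for both paper forms and database entries. Section B shows the group, so the assessment stays unblinded to arm. The lock removes knowledge of the outcome.

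**Section 3.6.** Define the primary analysis as all randomised patients with a day-1 score, analysed as allocated. Exclusion of deviators becomes a sensitivity analysis only. Complete SPIRIT item 20c to match.

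**Reconciliation.** Bring the WHO data set (1.1.2) and 3.2.5 into line with 3.2.2 on off-protocol treatment. Reword the incomplete-record exclusion in 3.2.2 and 3.8 so that a gap in the Data Collection Form does not remove a patient who has a day-1 score.

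**Cost.** A second file and a few paragraphs, with no added staff: Section B already arrives at the end of the procedure, and the assistant already checks day-1 forms. The small downside is that queries on day-1 forms go through the assistant. The Chief Researcher's check of day-1 data entry, the only second check described, waits until the assessment is locked, but it is kept.

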3.7.2 Interim Analysis

Interim analysis will not be done.

3.7.3 Harms

Adverse events will be recorded on the Data Collection Form. The form makes provision for expected adverse events (bronchospasm, laryngospasm, nausea & vomiting and/or other), as well as for unexpected adverse events. Treating anaesthetists will be instructed to report all adverse events to the Chief Researcher as soon as possible.

Both the control and interventional drugs have been extensively studied and used safely in clinical practice. A brief description of their side-effect profiles, which are very similar, can be found in the literature review. It is therefore not foreseen that many unexpected adverse events will occur. The purpose of the study is not to determine frequency or severity of adverse events, but it is acknowledged that adverse events may occur, and therefore monitoring is important.

Patients with known or suspected susceptibility to Malignant Hyperthermia are excluded from participation in the trial. In the unlikely event that a patient presents with signs and symptoms suggestive of Malignant Hyperthermia, treating anaesthetists will be instructed to stop all volatile agents and to follow departmental emergency management protocols.

3.8 Reliability and Validity

- Validity:
 - Internal validity should be assured on the basis that the anaesthetic techniques will be unchanged between the two groups, except for the anaesthetic vapour. Maintaining the end-tidal vapour concentration at 1MAC for both drugs will prevent disproportionate effects of one drug over the other. The patient population should be homogenous, as only ASA I and II patients presenting for ophthalmological surgery will be included in the study.
 - The chief researcher will counsel each treating anaesthetist prior to them starting a study case to ensure that they follow the required standardised anaesthesia protocol. This will reduce the

chance of protocol violations occurring. Any deviations from the standardised protocol will be recorded on the Data Collection Form and will be assessed by the chief researcher.

- Construct and content validity are assured on the basis that the QoR-15 has been extensively validated in many different languages and for many different surgery types.
- Data on the Case Report Forms will be inspected for completeness as per section 4.3.5. Incomplete cases will be excluded from analysis.

- Reliability:

- The QoR-15 is a reliable tool to use. During development of the tool, the internal consistency was measured using Cronbach α and split-half reliability, both of which had satisfactory results.
- Reproducibility of the QoR-15 was excellent, and exceeded that reported for the QoR-40, indicating that the QoR-15 score can be interpreted with confidence.

3.9 Bias

Randomisation bias will be avoided by using computer randomisation of patients to either the desflurane or isoflurane groups. The randomisation process will be managed by the statistician who is not involved in patient care. Block randomisation will be done to ensure that an equal number of patients are assigned to each treatment arm.

Selection bias will be reduced by using random block sizes and keeping the chief investigator, research assistant and treating anaesthetists blind to the size of each block.

Response or recall bias is possible with the use of a self-reporting questionnaire. To minimise this, the QoR-15 questionnaire will be administered on Day 1 post-operatively, prior to discharge, which will prevent poor memory recall. Blinding of patients will also help to minimise recall bias. Furthermore, the use of a validated scoring tool that uses clear statements and easy-to-understand scoring, like the QoR-15, should also minimise recall bias.

Observer bias will be limited by the observer who will administer the post-operative questionnaire being blinded to the treatment groups.

The QoR-15 has a score range of 0-150, and it was found not to be limited in its capacity to discriminate patients at the extremes of poor and good recovery. A floor or ceiling effect would therefore be unlikely.

4 Ethics and Dissemination

Informed consent will be taken from all participants by the Chief Researcher. Consent forms will be available in English, Afrikaans and Setswana. Only adult patients who can consent to participation will be included in the study.

A patient information leaflet explaining the objectives of the study in layman's terms has been developed (see Appendix 6.3). This leaflet has been translated into Setswana and Afrikaans. A copy of the patient information leaflet will be given to each patient.

The only document to contain the patient's name will be the sequentially numbered list that will be completed at recruitment. This list will be stored securely by the Chief Researcher. All data will be de-identified: no personal patient information (for example name, date of birth and file number) will be recorded on any study documents (Data Collection Form and QoR-15 forms). Study documents will be numbered sequentially (Data Collection Form and QoR-15 forms for each patient will have the same number). Paper records will be read into the REDCap System in sequence to ensure the study numbers and the electronic record numbers correspond. All paper documents will be stored securely by the Chief Researcher.

Patients will receive the same standard anaesthesia care, irrespective of which group they are randomised to.

Desflurane is registered at the MCC for the maintenance of anaesthesia. Desflurane is freely available in South Africa and will be used for the registered indication in this study.

Permission to perform the study at [name] Academic Hospital has been obtained from the hospital superintendent. Approval has obtained from the SMU Research Committee, as well as from the SMU Research Ethics Committee. The SMUREC Ethics Reference Number for the study is: SMUREC/M/240/2019:PG. The trial has been submitted for registration with the National Health Research Database (NHRD). A Notification of Phase IV trial was submitted to the South African Health Products Regulatory Authority, with reference number N20210205. The trial has been registered on ClinicalTrials.gov, with reference number NCT04188314.

Any important changes to the protocol after approval (e.g. changes to eligibility criteria, outcomes or analyses) will be communicated to the SMU Research Committee and the SMU Research Ethics Committee.

The results of the trial will be written up by the Chief Researcher for publication in a peer-reviewed academic journal. All supporting documents and de-identified data will be appended as supplements to the main publication. The results will also be presented at the annual SMU Research Day, and at the annual SASA conference, if selected for presentation.

The Chief Researcher holds current certification in Good Clinical Practice. There are no financial or competing interests for the Chief Researcher. There is no industry involvement in this trial.

5 References

6.1 SPIRIT Statement Checklist

SPIRIT 2013 Checklist: Recommended items to address in a clinical trial protocol and related documents*

Section/item	Item No	Description	Addressed on page number
Administrative information			
Title	1	Descriptive title identifying the study design, population, interventions, and, if applicable, trial acronym	Front page
Trial registration	2a	Trial identifier and registry name. If not yet registered, name of intended registry	2
	2b	All items from the World Health Organization Trial Registration Data Set	2-3
Protocol version	3	Date and version identifier	3
Funding	4	Sources and types of financial, material, and other support	4
Roles and responsibilities	5a	Names, affiliations, and roles of protocol contributors	2
	5b	Name and contact information for the trial sponsor	n/a
	5c	Role of study sponsor and funders, if any, in study design; collection, management, analysis, and interpretation of data; writing of the report; and the decision to submit the report for publication, including whether they will have ultimate authority over any of these activities	n/a
	5d	Composition, roles, and responsibilities of the coordinating centre, steering committee, endpoint adjudication committee, data management team, and other individuals or groups overseeing the trial, if applicable (see Item 21a for data monitoring committee)	n/a
Introduction			
Background and rationale	6a	Description of research question and justification for undertaking the trial, including summary of relevant studies (published and unpublished) examining benefits and harms for each intervention	5-9
	6b	Explanation for choice of comparators	8-9
Objectives	7	Specific objectives or hypotheses	9
Trial design	8	Description of trial design including type of trial (eg, parallel group, crossover, factorial, single group), allocation ratio, and framework (eg, superiority, equivalence, noninferiority, exploratory)	10
Methods: Participants, interventions, and outcomes			
Study setting	9	Description of study settings (eg, community clinic, academic hospital) and list of countries where data will be collected. Reference to where list of study sites can be obtained	10
Eligibility criteria	10	Inclusion and exclusion criteria for participants. If applicable, eligibility criteria for study centres and individuals who will perform the interventions (eg, surgeons, psychotherapists)	10-11
Interventions	11a	Interventions for each group with sufficient detail to allow replication, including how and when they will be administered	11-14
	11b	Criteria for discontinuing or modifying allocated interventions for a given trial participant (eg, drug dose change in response to harms, participant request, or improving/worsening disease)	n/a
	11c	Strategies to improve adherence to intervention protocols, and any procedures for monitoring adherence (eg, drug tablet return, laboratory tests)	14-16, 23
	11d	Relevant concomitant care and interventions that are permitted or prohibited during the trial	11-14
Outcomes	12	Primary, secondary, and other outcomes, including the specific measurement variable (eg, systolic blood pressure), analysis metric (eg, change from baseline, final value, time to event), method of aggregation (eg, median, proportion), and time point for each outcome. Explanation of the clinical relevance of chosen efficacy and harm outcomes is strongly recommended	17
Participant timeline	13	Time schedule of enrolment, interventions (including any run-ins and washouts), assessments, and visits for participants. A schematic diagram is highly recommended (see Figure)	18-19

1

2

Sample size	14	Estimated number of participants needed to achieve study objectives and how it was determined, including clinical and statistical assumptions supporting any sample size calculations	20
Recruitment	15	Strategies for achieving adequate participant enrolment to reach target sample size	20

Methods: Assignment of interventions (for controlled trials)

Allocation:

Sequence generation	16a	Method of generating the allocation sequence (eg, computer-generated random numbers), and list of any factors for stratification. To reduce predictability of a random sequence, details of any planned restriction (eg, blocking) should be provided in a separate document that is unavailable to those who enrol participants or assign interventions	20
Allocation concealment mechanism	16b	Mechanism of implementing the allocation sequence (eg, central telephone; sequentially numbered, opaque, sealed envelopes), describing any steps to conceal the sequence until interventions are assigned	20-21
Implementation	16c	Who will generate the allocation sequence, who will enrol participants, and who will assign participants to interventions	20-21
Blinding (masking)	17a	Who will be blinded after assignment to interventions (eg, trial participants, care providers, outcome assessors, data analysts), and how	21
	17b	If blinded, circumstances under which unblinding is permissible, and procedure for revealing a participant's allocated intervention during the trial	21

Methods: Data collection, management, and analysis

Data collection methods	18a	Plans for assessment and collection of outcome, baseline, and other trial data, including any related processes to promote data quality (eg, duplicate measurements, training of assessors) and a description of study instruments (eg, questionnaires, laboratory tests) along with their reliability and validity , if known. Reference to where data collection forms can be found, if not in the protocol	21-22
	18b	Plans to promote participant retention and complete follow-up, including list of any outcome data to be collected for participants who discontinue or deviate from intervention protocols	25-26
			22

3

Data management	19	Plans for data entry, coding, security, and storage, including any related processes to promote data quality (eg, double data entry; range checks for data values). Reference to where details of data management procedures can be found, if not in the protocol	22-23
Statistical methods	20a	Statistical methods for analysing primary and secondary outcomes. Reference to where other details of the statistical analysis plan can be found, if not in the protocol	24
	20b	Methods for any additional analyses (eg, subgroup and adjusted analyses)	24
	20c	Definition of analysis population relating to protocol non-adherence (eg, as randomised analysis), and any statistical methods to handle missing data (eg, multiple imputation)	n/a

Methods: Monitoring

Data monitoring	21a	Composition of data monitoring committee (DMC); summary of its role and reporting structure; statement of whether it is independent from the sponsor and competing interests; and reference to where further details about its charter can be found, if not in the protocol. Alternatively, an explanation of why a DMC is not needed	25
	21b	Description of any interim analyses and stopping guidelines, including who will have access to these interim results and make the final decision to terminate the trial	25
Harms	22	Plans for collecting, assessing, reporting, and managing solicited and spontaneously reported adverse events and other unintended effects of trial interventions or trial conduct	25
Auditing	23	Frequency and procedures for auditing trial conduct, if any, and whether the process will be independent from investigators and the sponsor	n/a

4

Ethics and dissemination

Research ethics approval	24	Plans for seeking research ethics committee/institutional review board (REC/IRB) approval	27
Protocol amendments	25	Plans for communicating important protocol modifications (eg, changes to eligibility criteria, outcomes, analyses) to relevant parties (eg, investigators, REC/IRBs, trial participants, trial registries, journals, regulators)	27

4

Consent or assent	26a	Who will obtain informed consent or assent from potential trial participants or authorised surrogates, and how (see Item 32)	27
	26b	Additional consent provisions for collection and use of participant data and biological specimens in ancillary studies, if applicable	
Confidentiality	27	How personal information about potential and enrolled participants will be collected, shared, and maintained in order to protect confidentiality before, during, and after the trial	27
Declaration of interests	28	Financial and other competing interests for principal investigators for the overall trial and each study site	27
Access to data	29	Statement of who will have access to the final trial dataset, and disclosure of contractual agreements that limit such access for investigators	n/a
Ancillary and post-trial care	30	Provisions, if any, for ancillary and post-trial care, and for compensation to those who suffer harm from trial participation	n/a
Dissemination policy	31a	Plans for investigators and sponsor to communicate trial results to participants, healthcare professionals, the public, and other relevant groups (eg, via publication, reporting in results databases, or other data sharing arrangements), including any publication restrictions	27
	31b	Authorship eligibility guidelines and any intended use of professional writers	27
	31c	Plans, if any, for granting public access to the full protocol, participant-level dataset, and statistical code	27
Appendices			
Informed consent materials	32	Model consent form and other related documentation given to participants and authorised surrogates	34-36 37-39
Biological specimens	33	Plans for collection, laboratory evaluation, and storage of biological specimens for genetic or molecular analysis in the current trial and for future use in ancillary studies, if applicable	n/a

*It is strongly recommended that this checklist be read in conjunction with the SPIRIT 2013 Explanation & Elaboration for important clarification on the items. Amendments to the protocol should be tracked and dated. The SPIRIT checklist is copyrighted by the SPIRIT Group under the Creative Commons "Attribution-NonCommercial-NoDerivs 3.0 Unported" license.

